13.1.5 Analysis plan for primary efficacy endpoint

Progression-free survival estimates will be determined using nonparametric maximum likelihood estimation for interval censored data. The generalized log-rank test for interval censored data will be used to assess whether PFS differs between the treatment arms (1,2). A secondary analysis of the primary clinical endpoint will follow the approach proposed by Freidlin et al. using scan times of 3 and 6 months [43].

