4.6 Patient Registration/Randomization procedure

If the local pathology assessment finds that the patient **does** have ER positive, HER2 negative disease, CRA will enter the Alliance ID number obtained at pre-registration and the stratification factors into the OPEN registration system and obtain a treatment assignment. The CRA will also enter the Alliance ID number obtained at pre-registration; upload a copy of the local pathology report, de-identified (but including the patient's Alliance ID number), into RAVE for documentation of estrogen receptor and HER2 status; complete the end of pre-registration phase case report forms as well as the baseline patient status case report forms and submit the research tissue cores.

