4.8 Stratification Factors and Treatment Assignments

Endocrine resistant disease

- 1) Primary endocrine resistant disease*
- 2) Secondary endocrine resistant disease**

Prior CDK 4/6 inhibitor and/or everolimus

- 1) Prior CDK 4/6 inhibitor or everolimus or both
- 2) No prior CDK 4/6 inhibitor and no prior everolimus

Disease type

- 1) Measureable by RECIST criteria
- 2) Bone only disease

*Primary endocrine resistant disease is defined as one of the following:

- Recurrence within the first 2 years of adjuvant endocrine therapy while on aromatase inhibitor therapy
- Progression within the first 6 months of initiating first-line endocrine therapy (either aromatase inhibitor or fulvestrant containing regimen) for the treatment of metastatic breast cancer.

**Secondary Clinical Resistance is defined as one of the following:

- Recurrence after year 2 while receiving adjuvant aromatase inhibitor therapy, or within 12 months of completing adjuvant aromatase inhibitor therapy.
- Progression occurring 6 or more months after initiating the first endocrine therapy for metastatic disease (either fulvestrant or aromatase inhibitor containing regimens).

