13.0 STATISTICAL CONSIDERATIONS**13.1 Study Design**

A randomized phase II clinical trial design was chosen to assess whether Z-Endoxifen HCl shows promise in providing greater in antitumor activity (in terms of increasing progression-free survival) than tamoxifen in postmenopausal women with metastatic ER positive breast cancer that is endocrine resistant.

This study will use a dynamic allocation procedure to allocate an equal number of patients to each of the treatment arm. This procedure will balance the marginal distributions of the stratification factors between these treatment arms. The stratification factors that will be used are: prior palbociclib and/or everolimus, type of disease and degree of endocrine resistance (see Section [4.8](#)).

All patients meeting the eligibility criteria who have signed a consent form and have begun treatment will be evaluable for assessment of all of the clinical endpoints. Patients will be included in the treatment group they were randomized to regardless of their actual treatment or duration of treatment. Summary statistics for patient and tumor characteristics, eligibility rates, length of follow-up, and treatment acceptance rates will be calculated by assigned treatment arm.

13.1.2 Definition and documentation of primary endpoint.

The primary endpoint is progression-free survival (PFS) defined as the time from randomization to documentation of local, regional or distant disease progression or death without progression of disease.

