13.1.3 Sample Size, Accrual Time and Study Duration

This trial was designed under the assumption that the median progression-free survival time among patients receiving tamoxifen is 3.0 months. Disease assessments in this trial are made at a frequency that is half the hypothesized median of the tamoxifen arm. Stone et al [41, 42] (2, 3) found that when disease assessments are made at a frequency that is half the control median, the difference in power between the log-rank test (with documented progression times) and generalized log-test with interval censored data was < 3%. As such we will determine the sample size assuming a log-rank test will be used with one-sided alpha=0.10 and power=95% so that the interval censored approach with the generalized log-rank test will have a power of > 90%.

With a sample size of 80 eligible patients (40 per treatment arm randomized in equal numbers) over a 15 month period and followed at least another 9 months after the close of enrollment before analysis is undertaken, a one-sided alpha=0.10 generalized log-rank test will have at least a 90% chance of detecting a 50% decrease in hazard of disease progression with Z-Endoxifen HCl relative to tamoxifen.

That corresponds to being able to detect an increase in the median PFS time from 3.0 months with tamoxifen to 6.0 months with Z-Endoxifen HCl.

An additional 14 patients will be screened to account for ineligible patients (tumors that are ER negative on biopsy) and those who cancel participation prior to starting treatment.

As of November 1, 2016, 24 (30%) of the 81 patients enrolled on this trial were found to have ER negative and/or HER2 positive breast cancer, a second primary cancer, or benign disease, making them ineligible. Therefore, the number of patients needed to be screened to obtain 80 eligible patients will be increased from 94 to 115 patients.

The efficacy analysis will be conducted when at least 72 patients have provided documentation of local, regional or distant disease progression or death without progression of disease.

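### The primary PFS test uses none of the three factors balanced at allocation: a small efficiency loss if they predict PFS, not a validity error

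*Combined protocol and SAP*

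**What the plan says.** Section 13.1 describes dynamic allocation and its aim: "This procedure will balance the marginal distributions of the stratification factors between these treatment arms". It lists the factors as "prior palbociclib and/or everolimus, type of disease and degree of endocrine resistance" and points to Section 4.8, which gives each factor two levels. There, the first level of the prior-therapy factor reads "Prior CDK 4/6 inhibitor or everolimus or both". Under Section 4.6 the site enters "the stratification factors into the OPEN registration system and obtain a treatment assignment", so the values are recorded at randomization.

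Section 13.1.3 sizes the trial on a two-arm comparison: "a one-sided alpha=0.10 generalized log-rank test will have at least a 90% chance of detecting a 50% decrease in hazard". It equates this with being able to "detect an increase in the median PFS time from 3.0 months with tamoxifen to 6.0 months with Z-Endoxifen HCl". An ordinary log-rank test is sized at 95% power so that the interval-censored version keeps more than 90%.

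For the primary analysis, Section 13.1.5 says: "The generalized log-rank test for interval censored data will be used to assess whether PFS differs between the treatment arms". It adds a secondary analysis at scan times of 3 and 6 months. Neither section names strata or covariates, and no other section gives an adjusted PFS comparison between arms. The remark on covariates in 13.2.2 concerns the exploratory DNA-alteration models. Section 13.1 limits the analysis set to eligible patients "who have signed a consent form and have begun treatment will be evaluable for assessment of all of the clinical endpoints", so it can be smaller than the set allocated.

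**The concern.** Balancing prognostic factors removes part of the chance variation between arms. A test that ignores the factors still counts that variation in its variance, so its p-value is too large on average. Separately, if the treatment effect is constant within factor levels, pooling levels with different hazards pulls the overall HR towards 1. Both effects cost power. At stake is part of the cushion between the 95% used for sizing and the 90% promised, that is, a somewhat higher chance of missing a useful drug.

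Any use of the factors also meets two unclear definitions.
- Section 13.1 names palbociclib where Section 4.8 has any CDK 4/6 inhibitor. Section 3.2.9 admits prior abemaciclib or ribociclib too, so such a patient without everolimus falls in different levels under the two wordings.
- Section 4.8 gives disease type only measurable and bone-only levels. Section 3.3.1 also admits patients with non-measurable disease plus bone metastases, whose level is not stated.

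**Working it through.** **1. The plan's own figure.** Inputs from 13.1.3: HR 0.5, one-sided alpha 0.10, 95% power, 1:1 allocation. Schoenfeld events = 4(z₀.₉₀ + z₀.₉₅)²/(ln HR)² = 4(1.2816 + 1.6449)²/(0.6931)² = 71.3, rounded up to 72. Power at 72 events = Φ(√72 × 0.6931/2 − 1.2816) = Φ(1.659) = 95.1%. With exponential medians of 3 and 6 months, 15 months of uniform accrual and 9 more of follow-up, event probabilities are 0.965 and 0.832, so 40 × (0.965 + 0.832) = 71.9 events are expected. The design reproduces.

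**2. Main simulation.** From the protocol: 80 analysed patients, 15-month accrual, overall tamoxifen median 3.0 months, scans as in 11.1 (weeks 6, 12, 18, 24, then every 12), analysis at the 72nd detected event. Assumed: three independent binary factors with prevalences 35/50/30%, the factor HRs below, and Pocock-Simon minimization with a 0.9 coin. The tests are grouped-data proportional hazards score tests. There were 40,000 runs per cell (standard error about 0.15 point). Entries are percentages; gains are in points.

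| Factor HRs | 1 each | 1.5 each | 2/1.7/1.5 | 2 each |
|---|---|---|---|---|
| Planned test, size | 10.5 | 9.7 | 9.0 | 8.4 |
| Adjusted, size at cut-off 1.28 | 11.1 | 10.9 | 10.9 | 10.8 |
| Adjusted, size at cut-off 1.35 | 10.0 | 9.7 | 9.7 | 9.6 |
| HR 0.5 within levels: planned power | 94.8 | 93.0 | 91.6 | 89.9 |
| HR 0.5 within levels: adjusted power (1.35) | 94.0 | 93.9 | 93.9 | 93.9 |
| Difference, adjusted minus planned | −0.8 | 0.9 | 2.3 | 4.0 |
| Gain at equal size | −0.5 | 0.8 | 1.6 | 2.5 |
| Overall HR 0.5: planned power | 94.8 | 95.5 | 96.1 | 96.5 |
| Overall HR 0.5: gain at equal size | −0.5 | 0.6 | 0.9 | 1.2 |

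The planned test's 10.5% in the first column arises with no factor effects at all, so it cannot come from ignoring the factors.

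**3. Which HR is 0.5.** Halving every patient's exponential hazard doubles every PFS time, so a within-level HR of 0.5 moves the overall median exactly from 3.0 to 6.0 months. The overall HR is then 0.527, 0.546 and 0.565 in the three prognostic settings. An overall HR of 0.5 needs within-level HRs of 0.472, 0.453 and 0.433, and gives an endoxifen median of 6.35 to 6.93 months. Section 13.1.3 does not say which is meant.

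**4. Second simulation.** This used log-rank and Cox tests on grouped times as stand-ins, a 0.85 coin, the same prevalences, a data cut at 24 months, and 6-weekly scans to week 36 (denser than either schedule in the protocol). For factor HRs of 1.0, 1.3, 1.5 and 2.0 each, with HR 0.5 within levels:
- unadjusted power 94, 94, 92 and 88%, with size about 10, 9.5, 8.7 and 7.6%;
- main-effects adjusted power 94, 94, 94 and 93%, with size 9.8 to 10.5% at the usual cut-off;
- 8-cell stratified power 91, 91, 90 and 90%.

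The 88% comes from about 68 events, not the 72 that 13.1.3 requires. By the formula in step 1, 67.7 events give Φ(1.570) = 94.2% against 95.1%, so about 1 point of that deficit is the earlier cut.

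**5. Sensitivity.**
- With 88 randomized and 8 excluded at random before treatment, planned power in the main model is 94.7, 92.8, 91.1 and 89.2%.
- With HR 2 each, it is 91.1% at prevalences 20/30/15% (gain at equal size 1.4 points) and 90.6% at 20/50/20%.
- With only one factor at HR 2, it is 92.7%.

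**6. Form of adjustment.** Eight cells leave 80/8 = 10 patients per cell. The 8-cell test had size 11.9 to 12.1% in the main simulation, and cost about 3 points of power in the second when the factors were not prognostic (91 against 94%). Main effects match the marginal balancing and avoid this.

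**The case against.** The strongest reply is that nothing here is an error. An unadjusted log-rank test is a legitimate choice for an 80-patient phase II screen, and the plan bought a cushion by sizing at 95%. A power below 90% appears only if HR 0.5 is read as a within-level effect and all three factors have HR 2 at the assumed prevalences. The main model's 89.9% (standard error 0.15) cannot be told apart from 90%. At equal size the gain runs only from −0.5 to 2.5 points. All of this stands, and it sets the grade.

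Two practical objections also stand. First, an adjusted test is model-based, and its size depends on its form: the score test ran near 11% at 1.28, the Cox test at 9.8 to 10.5%. A fixed cut-off taken from these simulations would rest on an assumed allocation scheme, since 13.1 says only that allocation is dynamic. Second, endoxifen supplies are open label (10.1.1), and statisticians prepare efficacy reports (13.1.7). By November 1, 2016, 81 patients were enrolled, 24 of them ineligible, leaving at most 57 towards the 80. An unconditional change of primary test would be open to challenge.

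The factor definitions do not affect the planned test. A model using values as entered could be fitted before they are reconciled, but the meaning of those values would be unclear for some patients.

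What survives is narrow: three factors already collected and balanced go unused, and using them costs little.

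A reader might infer that dynamic allocation makes the unadjusted test invalid. It does not: the distortion is conservative. A reader might also infer that balancing on factors obliges a stratified primary test. No section says so, and 13.1.3 sizes the trial on the unadjusted one.

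**Conclusion.** The point holds as a minor matter of efficiency, worth considering. If the factors predict PFS, the planned test's true size is about 8 to 10% at nominal 10%. With HR 0.5 within levels, the power forgone is about 0 to 1 point for weak factors and up to about 3 to 5 points for three strong ones. With overall HR 0.5, planned power is 94.8 to 96.5%.

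The direction is secure. The size rests on assumed factor HRs, prevalences, independence of the factors and exponential PFS. A reader might infer that the trial is underpowered. The documents do not support that: they give no prognostic effects, and power near or just under 90% needs the strongest setting examined together with the within-level reading. Nor do the two wordings of the prior-therapy factor show that any patient was misallocated. They show only that the definitions should agree.

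**What to change.** In 13.1.5, pre-specify a one-sided 0.10 treatment comparison from an interval-censored proportional hazards model, with the three Section 4.8 factors as main effects coded as entered at randomization. Do not use an 8-cell stratified test.

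- If those deciding have not seen PFS by arm, the adjusted test may be primary, with the generalized log-rank test as a sensitivity analysis. The sponsor should first confirm the one-sided size with its own allocation settings and test form, and calibrate if needed. No cut-off should be fixed from the simulations above.
- If the decision is not blind to PFS by arm, keep the log-rank test as primary and report the adjusted test as a pre-specified sensitivity analysis.

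Also reconcile the prior-therapy wording in 13.1 with 4.8, and state the disease-type level for patients with non-measurable disease plus bone metastases.

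The cost is about one paragraph and no new data. The downsides are reliance on a model and under 1 point of power lost if the factors are not prognostic (94.0 against 94.8%). Events and sample size do not change.

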13.1.6 Secondary Clinical Endpoints

13.1.6.1 Adverse Events

Per CTEP Version 4.0 of the NCI CTCAE, an adverse event (AE) is any unfavorable and unintended sign (including an abnormal laboratory finding), symptom, or disease temporally associated with the use of a medical treatment or procedure that may or may not be considered related to the medical treatment or procedure. All grade 2, 3, 4 or 5 adverse events will be documented and assigned an attribute by treating clinician as to its relationship to treatment.

Note: Serious adverse events will be reported on CTEP-AERS using CTCAE v5.0.

For a given AE, the proportion of patients on each treatment arm who report developing a grade 2-5 of this AE will be determined.

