2.2 Secondary Objectives

- 2.2.1 To assess the safety profile of each of these agents in this patient population.
- 2.2.2 To assess whether the tumor response rate (as determined using the RECIST criteria) among those randomized to Z-endoxifen HCl differs from that among those randomized to tamoxifen.
- 2.2.3 To estimate the median progression-free survival time for those who receive Z-Endoxifen HCl after disease progression with tamoxifen.

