4.9 Re-registration at the Time of Progression

Patients who meet the RECIST criteria for disease progression during tamoxifen treatment may switch to Z-Endoxifen HCl until disease progression is documented. Please note that patients who opt to cross over must be re-registered to the study within 14 days of progression documentation.

Re-registration procedures:

OPEN may be accessed at <https://open.ctsu.org>, from the OPEN tab on the CTSU website at <https://www.ctsu.org>.

To enroll a patient within OPEN, institution staff must have:

1. A valid and active CTEP-IAM account. This is the same user ID and password used for CTSU's website (for more information see https://www.ctsu.org/public/CTEP-IAM_Factsheet.pdf).
2. Enrollment of patients on Alliance A011203 coordinated protocols requires a "Registrar" role in the ALLIANCE roster. Assignment of the "Registrar" role is managed through the Alliance Central Office.

The OPEN system will provide the registering site with a printable confirmation of re-registration. Please print the confirmation for your records. Further instructional information is provided on the CTSU members' website OPEN tab, or within the OPEN URL. For any additional questions, contact the CTSU Help Desk at [name], or [contact].

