5.2 Study Arm 2 Tamoxifen

	Prior to pre-registration	Pre-registration on Period (any time during days -28 to -1)	Tamoxifen treatment phase		Z-Endoxifen HCl Crossover phase	
			Days 1 of each treatment cycle	At PD or or discontinuation of tamoxifen **	Day 1 of each treatment cycle	At PD, or discontinuation of Z-Endoxifen HCl **
Tests & Observations						
History and physical, weight, PS	X		X	X	X	X
Height	X					
Pulse, Blood Pressure	X		X	X	X	X
Adverse Event Assessment			X	X	X	X
Patient Medication Log			X(1)	X(1)	X(1)	X(1)
Registration Fatigue/Uniscale Assessment		A				
Standard of care biopsy of either locally recurrent or metastatic breast cancer for determination of ER, PR and HER2 in metastatic disease specimen		B				
Laboratory Studies						
AST, creatinine, Total Bilirubin	X	X	X	X	X(2)	X, G
Complete Blood Count, Differential, Platelets	X	X	X	X	X(2)	X, G
Albumin, Alk Phos, ALT, calcium, glucose, phosphorous, sodium, potassium		X	X	X	X(2)	X, G
Fasting lipid profile (total Cholesterol, LDL, HDL, triglycerides)		C	C		C	
Imaging Tumor Measurements/Evaluation of Indicator Lesions						
CT/MRI		D, E, F	D, E		D, E(3)	D, E, G
Bone Scan/PET-CT scan		D, E, F	E		E(3)	E, G
Correlative Studies: For Patients who consent to participate						
Tissue and Blood samples	See Sections 6.0 and 14.0 .					

* Cycle length is 21 days. Labs completed prior to registration may be used for day 1 of cycle one tests if obtained ≤ 21 days prior to treatment. For subsequent cycles, labs, scans, tests and observations may be obtained no more than +/- 3 days prior to day 1 of treatment.

** Patients who progress on tamoxifen may crossover to Z-Endoxifen HCl treatment. Patients will be followed for disease outcome during Z-Endoxifen HCl treatment phase where the baseline tumor measurement is considered to be the tumor size at disease progression on tamoxifen. Following the discontinuation of Z-Endoxifen HCl, patients will be followed yearly for a maximum of 5 years from randomization. Future treatment is at the discretion of patient's physician.

Patients who choose not to crossover to Z-Endoxifen HCl will be followed yearly for a maximum of 5 years from randomization. Future treatment is at the discretion of patient's physician (see Section [12.3](#)).

1. Medication Log must begin on the day the patient begins study medication and must be completed per protocol (see Section [7.4](#)).

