10.1.7 Adverse events

The most common adverse effects of Z-Endoxifen HCl have been mostly grades 1-2 hot flashes (50%), anemia (25%), fatigue (25%), lymphocyte count decreased (22%), nausea (19%), platelet count decreased (19%), hypertriglyceridemia (16%), irritability (16%), anorexia (13%), AST increased (13%), edema limbs (13%), and WBCs decreased (13%).

Thromboembolic event (grades 3-4) and hypertriglyceridemia (grade 4) have also been reported.

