12.3 Discontinuation of Protocol Therapy

Reasons why the protocol therapy may be discontinued:

- Tumor progression
- Request by the patient to withdraw
- Unacceptable toxicity
- Inter-current illness
- Administration of alternative treatment

Arm 1 patients:

Patients who discontinue treatment for any of the above reasons will proceed to event monitoring. Patients will be followed yearly for a maximum of 5 years from study registration. Once a patient has discontinued study treatment, future therapy is at the discretion of the treating physician.

Arm 2 patients:

Patients randomized to tamoxifen who progress during tamoxifen treatment may choose to switch to Z-Endoxifen HCl and continue on Z-Endoxifen HCl until disease progression is noted. After disease progression during Z-Endoxifen HCl treatment patient will proceed to event monitoring. Patients will be followed yearly for a maximum of 5 years from study registration. Once a patient has discontinued study treatment, future therapy is at the discretion of the treating physician.

Patients who discontinue treatment for any of the above reasons other than progression or patients who refuse to crossover to Z-Endoxifen HCl will proceed to event monitoring. Patients will be followed yearly for a maximum of 5 years from study registration/randomization. Once a patient has discontinued study treatment, future therapy is at the discretion of the treating physician.

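### The AE summary in Section 13.1.6.1 sets no cut at crossover, so on its most direct reading Z-Endoxifen events after the switch count in the tamoxifen column, contrary to the by-agent safety objective.

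*Combined protocol and SAP*

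**What the plan says.** The safety objective, 2.2.1, is by agent: "To assess the safety profile of each of these agents in this patient population".

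The only AE summary in the statistical section is in 13.1.6.1: "the proportion of patients on each treatment arm who report developing a grade 2-5 of this AE will be determined". No time window, on-treatment period or cut at crossover is attached, and the proportion is not limited to events attributed to treatment.

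Section 13.1 sets the grouping: "Patients will be included in the treatment group they were randomized to regardless of their actual treatment or duration of treatment". The sentence before it concerns who is evaluable for all the clinical endpoints. Adverse events fall under 13.1.6, Secondary Clinical Endpoints.

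Crossover is built into Arm 2. The notes to the calendar in 5.2 say "Patients who progress on tamoxifen may crossover to Z-Endoxifen HCl treatment", and 12.3 says that such patients "may choose to switch to Z-Endoxifen HCl and continue on Z-Endoxifen HCl until disease progression is noted". The AE assessment row in 5.2 is marked in the two tamoxifen columns and in the two crossover columns, and Section 9.1 ties routine AE reporting to the calendars. Section 4.9 adds that "patients who opt to cross over must be re-registered to the study within 14 days of progression documentation". Objective 2.2.3 gives the crossover phase its own progression-free survival estimate. No AE counterpart is given.

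**The concern.** A table by randomised arm answers what happened to patients assigned to start on tamoxifen. Objective 2.2.1 asks what each drug does. The two questions part company once tamoxifen patients start taking Z-Endoxifen HCl while their events are still being collected.

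If post-switch events stay in the tamoxifen column, that column mixes two drugs. An excess of some event on Z-Endoxifen HCl is narrowed or even reversed. An excess on tamoxifen is widened. In a randomised phase II trial of an investigational agent, this AE comparison is one of the main products besides the primary endpoint. It would also leave the crossover patients' experience on Z-Endoxifen HCl without a table of its own.

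**Working it through.** **1. Which way the rules point.** Section 13.1 assigns the patient to the randomised arm, 13.1.6.1 counts any grade 2-5 event per arm without a window, and 5.2 with 9.1 keeps events coming in after the switch. Nothing in Section 13 separates the crossover phase for AEs. Followed together, these put a post-switch event in the tamoxifen numerator.

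**2. Direction.** The denominator (patients randomised to tamoxifen who began treatment) does not change when post-switch time is added. The numerator can only stay the same or grow. So the tamoxifen proportion cannot fall.

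**3. How many patients could cross over.** Section 13.1.3 says "The efficacy analysis will be conducted when at least 72 patients have provided documentation of local, regional or distant disease progression or death". The figure of 72 reproduces. The inputs are hazard ratio 0.5, one-sided alpha 0.10, power 95% and 1:1 allocation:

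- Schoenfeld: 4 × (1.2816 + 1.6449)² / (ln 2)² = 4 × 8.564 / 0.4805 = 71.3, rounded up to 72.

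With 40 per arm, the fewest tamoxifen events occur if all 40 Z-Endoxifen patients have had one: 72 − 40 = 32 of 40, or 80%.

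Under the plan's own medians (3 and 6 months, taken as exponential), 15 months of uniform accrual and 9 months of further follow-up, P(event) = 1 − [exp(−9λ) − exp(−24λ)] / (15λ), with λ = ln 2 / median:

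- Tamoxifen: 1 − (0.1250 − 0.0039) / 3.466 = 96.5%, about 38.6 of 40.
- Z-Endoxifen HCl: 1 − (0.3536 − 0.0625) / 1.733 = 83.2%, about 33.3 of 40.
- Total: 71.9, in line with 72.

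These counts bound the crossovers from above. Deaths without progression and refusals reduce them by an unknown amount.

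**4. Illustration only.** Let pT be the chance of a given event on tamoxifen, pE the chance on Z-Endoxifen HCl (the same in Arm 1 and after crossover), and c the share of Arm 2 that crosses over. Assuming independence, the pooled tamoxifen column is 1 − (1 − pT)(1 − c·pE). None of these inputs is in the documents.

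| pT | pE | c | By-agent difference (pE − pT) | Pooled tamoxifen column | Difference shown |
|---|---|---|---|---|---|
| 10% | 30% | 25% | +20 | 16.75% | +13.25 |
| 10% | 30% | 50% | +20 | 23.5% | +6.5 |
| 10% | 30% | 75% | +20 | 30.25% | −0.25 |
| 20% | 15% | 50% | −5 | 26.0% | −11.0 |

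The first three rows show a Z-Endoxifen excess narrowing and then reversing. The last shows a tamoxifen excess widening.

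**5. Why exposure must be shown as well.** Suppose both drugs have the same monthly event rate h = 0.02 (assumed), with exposure medians m of 6 and 3 months. The chance of an event on treatment is h / (ln 2/m + h). That is 0.02 / (0.1155 + 0.02) = 14.8% on Z-Endoxifen HCl and 0.02 / (0.2310 + 0.02) = 8.0% on tamoxifen. A by-agent table would show a gap of 6.8 points that comes from longer exposure alone.

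**The case against.** The strongest reply is that the plan is silent rather than wrong. Section 13.1.6.1 does not contain the word randomised; that comes from 13.1, whose sentence allocates patients to groups and sets no event window. Note G to the 5.2 calendar and Section 7.3 both refer to the Tamoxifen treatment arm as the period before crossover, in contrast to the Z-Endoxifen HCl phase. On that usage, an event on the arm could stop at the switch. The separate calendar columns, re-registration and the crossover medication log in Appendix III make a split possible. This stands to the extent that a reader who infers that the plan definitely pools the events goes further than the text. It does not remove the problem. The usage is incidental, 13.1 points the other way, and the plan's only AE rule should not depend on which one the analyst prefers.

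A reader might also infer a definite size by taking the percentages in 10.1.7 as crossover-phase rates. The documents do not support that. Those figures cover mostly grades 1-2, whereas the planned column is grades 2-5. Section 1.6 traces them to 32 patients in two phase I studies, the one described there covering 20 to 160 mg. No tamoxifen comparator rate is given.

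Two objections to a by-agent table also stand. With equal rates it shows a gap due to exposure alone (step 5), and patient-months make this visible without removing it. A cut at the first crossover dose can also misplace events. Section 10.2.6 gives tamoxifen a half-life of about 5 to 7 days and its main metabolite about 14 days. Section 7.3 allows up to 28 days between documented progression and the first crossover dose.

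**Conclusion.** The concern holds as a conflict between the AE rule on its most direct reading and objective 2.2.1, and as an ambiguity on any reading. The direction is certain if events are pooled: the tamoxifen proportions can only rise. The group from which crossovers come is large, at least 32 of 40 at the 72-event analysis, assuming 40 per arm and an AE table produced at that time. The size of the distortion cannot be derived from the documents, and the table in the working is illustrative.

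A reader might infer that the trial's comparison of the arms is compromised. It is not. The AE summary is descriptive, no planned test depends on it, and progression-free survival is measured before any switch. The point should be fixed before the safety tables are produced, because following the written rule gives a worse answer to a stated objective and the alternative is inexpensive.

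**What to change.** In 13.1.6.1, state that grade 2-5 adverse events are tabulated by the agent being taken at onset:

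- **Tamoxifen column:** ends at the first crossover dose of Z-Endoxifen HCl.
- **Crossover column:** shown separately, with patients who crossed over as denominator, counting only events that start or worsen in grade after that first dose.
- **Exposure:** patient-months on agent printed beside each column, so that longer exposure is not read as a higher rate.

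No extra visits, patients or tests are needed, since AEs are already assessed in both phases and crossover requires re-registration. The cost is wording and table layout, provided that first crossover dose dates and AE onset dates are in the trial database. The documents do not show this. Section 7.4 returns the medication log to the treating institution, and 9.1 names the AE forms without listing their fields. The sponsor should confirm both.

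The crossover column will be small and its proportions imprecise. Some early crossover events may be residual tamoxifen effects, and events between progression and the first crossover dose will fall in the tamoxifen column. A footnote should say so.
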